8.4 Reporting of a serious adverse event

In the event of a SAE, regardless of any opinions on relationship to the study drug, the Medical Monitor is to be notified. In the event that the Medical Monitor cannot be reached, other personnel will be available to receive the report.

All SAEs that are unexpected (i.e., not identified in nature, severity, or frequency in the current Investigator’s Brochure), whether considered to be drug related or not, require a SAE Report Form be completed. All SUSARS (suspected unexpected serious adverse events) must be reported in writing to the Concerned Research Ethics Board (REB).

A death occurring during the study or which comes to the attention of the Investigator within 30 days after discontinuation of study drug, whether considered treatment related or not, must be reported.

Preliminary reports of SAEs will be followed by detailed descriptions which will include copies of the hospital case reports, autopsy reports, and other documents as requested and applicable.

8.5 Reporting of a pregnancy during the study

In principle, pregnancy and the lactation period are exclusion criteria for clinical studies involving investigational drugs, which are not directly related to the respective conditions. In the event of a pregnancy occurring during the course of this particular study, the subject should be

withdrawn from study, but closely followed-up during the entire course of the pregnancy and postpartum period. All recommendations described in the investigational drug brochure during pregnancy and lactation have to be carefully considered.

Parental and neonatal outcomes must be recorded even if they are completely normal and without Adverse Events. Off-spring should be followed up for at least 8 weeks after delivery. Longer observation periods may be considered if an adverse outcome of the pregnancy was observed.

9. STATISTICAL ANALYSIS

9.1 Sample Size Selection

This is an exploratory proof of concept immunological study. As such the number of patients in each treatment group was arbitrarily chosen in lieu of a convenience sampling for this type of study.

9.2 Demographics

Demographic variables such as age, race, etc. and baseline status (medical history, physical exam, etc.) will be documented by dose level and/or overall, as applicable.

9.3 Biomarkers

We will analyze mean differences between two independent groups whilst subjecting participants to repeated measures overtime to assess variability between- and within-subjects variable. Therefore, we will use the mixed-design ANOVA model.

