- To evaluate the safety of FMT in MS patients
- To evaluate tolerability of FMT in MS patients

Trial Design:

The proposed randomized, open label, controlled [treatment as usual control group], crossover study will be conducted in 40 patients (n=20 per group) diagnosed with the relapsing forms of multiple sclerosis according to the McDonald 2010 Criteria¹.

Based on the diagnostic criteria patients will be further screened to confirm eligibility and if eligible then consented.

Patients will be randomized 1:1 into two groups. One group will receive FMT, done by rectal enema administered by a RN, at baseline, month 1, month 2, month 3, month 4, and month 5 (early intervention group). The other group will receive treatment as per standard of care (treatment as usual control group) in the beginning of the study. For the last 6 months they will also receive FMT at month 6, month 7, month 8, month 9, month 10, and month 11 (late intervention group).

Clinical visits for both groups will be performed at baseline, and months 1 to 12 inclusive. During these visits a physical exam with vital signs, including a standardized neurological assessment Expanded Disability Status Scale – EDSS) will be done.

Patient's stools will be collected before each FMT procedure in both groups to evaluate gut microbial composition.

Urine will be collected to evaluate gut permeability at baseline, 6 and 12 months for both groups.

Peripheral blood samples also will be collected to evaluate circulating cytokine levels (IL-1 β , IL-2, IL-4, IL-5, IL-6, IL-9, IL-10, IL-12p70, IL-13, IL- 15, IL-17A, IL-17E/IL-25, IL-17F, IL-21, IL-22, IL-23, IL-27, IL-28A, IL-31, IL-33, GM-CSF, IFN γ , MIP-3 α , TNF α and TNF β) at baseline, months 1 to 12 inclusive for both groups.

Peripheral blood samples will also be collected to evaluate blood DNA bacteria at baseline, and months 1 to 12 inclusive for both groups.

Brain MRI with gadolinium [3T MRI machine at Robarts Research Institute] will be performed at baseline, 6 and 12 months for both groups as a safety biomarker [to rule out paradoxical effects; i.e. significant increase in MS activity as defined by Cutter's rule: 5 or more newly enhancing white matter lesions in the brain compared to the previous scan].

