3.1 Primary outcome

To evaluate if FMT from healthy donors can significantly change cytokine profile in peripheral blood samples of RMS patients.

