4.2 Duration of therapy and study

Patients will be screened prior to starting treatment with FMT and randomized between 2 groups. One, early intervention group, will receive FMT for the first 6 months and the other will be a control group treated as standard only. After 6 months, the early intervention will not receive the transplantation anymore and the control group will receive FMT for the remaining 6 months. Study drug will be administered for a period of 6 months for each group total.

Patients may withdraw consent at any time. Study drug may be discontinued at any time by the investigator if doing so is deemed to be in the best interest of the patient. However, the patient should be encouraged to continue in the study for safety follow-up.

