6.3 Sample Size analysis

It was assumed that the acceptable Type I error will be 0.05 and power will be 0.8. Moderate effect size effect is expected. This is a study of a kind that has never been done before in this population. From similar studies in other populations or other interventions on a similar population, a 40% change in cytokine levels (ie TGFbeta1) analysis is expected, as reported on other cytokine study with no pharmacological intervention, such as vitamin D supplementation⁷³.

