7.0 ASSESSMENT OF EFFICACY

As this study is an immunological study, the following efficacy outcomes will be evaluated:

- Changes in peripheral blood cytokines within RMS patients between baseline and months 1 to 12 inclusive, for both groups. Luminex kit will be used.
- Changes on microbiome after FMT by analyzing the gut bacterial composition through stool analysis and blood bacteria DNA at baseline, and months 1 to 12 inclusive for both groups.
- Gut permeability through urine analysis at baseline, 6 and 12 months for both groups.

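### Section 9.3 analyses a crossover as a two-group comparison without saying which term or time window tests FMT; averaged over months 0–12, the group difference is a sequence contrast, not an FMT effect

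*Combined protocol and SAP*

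**What the plan says.** The question in Section 3.1 is: "To evaluate if FMT from healthy donors can significantly change cytokine profile in peripheral blood samples of RMS patients". Section 9.3 gives the only efficacy model: "We will analyze mean differences between two independent groups whilst subjecting participants to repeated measures overtime", by mixed-design ANOVA. It names no model term, contrast or window as the test of FMT.

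The Synopsis and Section 4 describe a randomised crossover with 20 patients per group. The early group receives FMT at months 0 to 5 and the late group at months 6 to 11. Section 4.2 adds: "Study drug will be administered for a period of 6 months for each group total". Section 7.0 defines the cytokine outcome as "Changes in peripheral blood cytokines within RMS patients between baseline and months 1 to 12 inclusive, for both groups", which is 13 samples per patient. Sections 6.2.1 and 6.2.2 place the blood sample before that visit's FMT.

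Section 6.2.3 adds two cytokine comparisons: patients against healthy volunteers at all time points, and patients at baseline against month 12.

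**The concern.** The model in 9.3 is that of a parallel-group trial, but here the two groups differ only in when they receive the same treatment. A group mean taken over the whole year therefore need not carry the FMT effect. In a crossover, treatment is identified by which samples follow FMT, and 9.3 has no term for that.

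The primary conclusion is at stake. Depending on the term and window chosen, the same data give tests that range from nearly blind to FMT to very sensitive to it. The study is open-label and measures 25 cytokines, and the wording leaves that choice open until the data have been seen. One literal reading could report no effect when a large but transient effect exists.

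**Working it through.** **The plan's own figure.** Section 6.3 says: "It was assumed that the acceptable Type I error will be 0.05 and power will be 0.8". The effect is given as "Moderate effect size effect is expected" and as "a 40% change in cytokine levels (ie TGFbeta1) analysis is expected", with no SD, numeric effect size or correlation, and Section 9.1 calls the group size arbitrary. The 0.8 therefore cannot be reproduced. If moderate means d = 0.5 (an assumption), a single two-sided two-group comparison needs 2(1.96 + 0.84)²/0.5² ≈ 63 per group, and 20 per group gives power of about 0.35. The plan states no power for any term of the ANOVA.

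**Exposed samples.** Because blood precedes the visit's FMT, samples taken after at least one FMT and within the course are:
- early group: months 1–6, which is 6 of 13;
- late group: months 7–12, which is 6 of 13 (its month-6 sample precedes its first FMT).

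**Expected early-minus-late difference, as a fraction of the effect d.** Over 13 visits, a purely on-treatment effect gives (6d − 6d)/13 = 0. Full persistence gives (12d − 6d)/13 = 0.46d.

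| After the early group's course, the effect… | 13-visit mean | Months 1–6 mean |
|---|---|---|
| is lost at once | 0 | 1.00 |
| halves every month | 0.08 | 1.00 |
| halves every 3 months | 0.22 | 1.00 |
| persists fully | 0.46 | 1.00 |

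**Power at d = 0.5, by simulation.** Assumptions: 20 per group, complete data, two-sided 0.05, and within-patient correlation either compound-symmetric 0.3–0.7 or AR(1) 0.8–0.9 per month. The documents give none of these correlations.

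| Test | Effect only during the course | Full persistence |
|---|---|---|
| Group mean over 13 visits | 4–7% | 13–24% |
| Group-by-visit interaction (12 df, Greenhouse–Geisser) | about 90–100% | about 33–93% |
| Group difference, months 1–6, baseline-adjusted | about 63–86% | the same (months 7–12 not used) |

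For an effect present only during the course, the 13-visit group mean also stayed at 4–6% rejection from d = 0.25 to d = 2.0 under compound-symmetric correlation 0.5 and 0.8.

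**Hand check at compound-symmetric correlation 0.5.**
- 13-visit mean, full persistence: variance per patient (1 + 12 × 0.5)/13 = 0.538; SE of the difference √(0.538 × 2/20) = 0.232; expected difference 0.46 × 0.5 = 0.231. The ratio is 1.00, so power is about Φ(1.00 − 1.96) = 17%.
- Months 1–6, baseline-adjusted: residual variance (1 + 5 × 0.5)/6 − 0.5² = 0.333; SE √(0.333 × 2/20) = 0.183; ratio 0.5/0.183 = 2.74. Power is about Φ(2.74 − 1.96) = 78%, slightly less with the t distribution.

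Both lie inside the simulated ranges.

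**The other planned cytokine comparisons.** At month 12 the early group is seven months past its last FMT (month 5) and the late group one month past its own (month 11). Everyone has been treated, so baseline against month 12 has no untreated control. The healthy-volunteer comparison does not isolate FMT either.

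**The case against.** The strongest reply is that 9.3 never names the group main effect, an overall mean or a months 0–12 average as the test of FMT. A mixed-design ANOVA also contains group-by-time, and that term has about 90–100% power at d = 0.5 in exactly the scenario where the main effect is blind. Section 4 calls the late group a control for the first six months, and over months 1–6 the group difference is the full FMT effect. The exact zero also needs the effect to vanish after the last FMT. The documents do not assume this: there is no washout, and Section 6.2.5 treats the time to microbial reversion as a question to be answered. Finally, Section 9.1 describes the study as exploratory.

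Much of this stands. A reader might infer that the plan's named test has 5% power whatever the effect size, or that the trial as planned cannot detect FMT. The documents do not support either reading.

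The reply does not close the gap. The interaction is an omnibus test that responds to any divergence of the two profiles, gives neither the direction nor the size of an FMT effect, and is not named. The months 1–6 window is not stated anywhere, while Section 7.0 runs to month 12. Exploratory status does not remove the need to say which comparison answers Section 3.1.

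**Conclusion.** The point holds as a failure to specify the FMT contrast, in a model that lacks the crossover structure. If the group difference in 9.3 is averaged over months 0–12, it is a sequence contrast. It recovers between 0 and 0.46 of the FMT effect, depending on persistence, with about 5% to 24% power at d = 0.5. The exposure counts and fractions follow from the schedule alone. The powers rest on the assumed d, the assumed correlations, 20 per group and complete data.

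What is not established is that the investigators intend that average as their test, or that the ANOVA as a whole is insensitive to FMT. The contrast defines the primary result, so it should be settled before analysis.

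**What to change.** In Section 9.3:

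1. Name as the primary FMT contrast the early-versus-late comparison over months 1–6, adjusted for baseline. It is randomised and needs no carryover assumption.
2. As a secondary analysis over months 0–12, use a mixed model with visit month as a fixed effect, a random patient effect, a stated within-patient correlation structure, and a time-varying FMT status: not yet treated, within the course, after the course. Report after-course against not-yet-treated as persistence. The within-course term has about 78–97% power at d = 0.5 under the same correlations, if the correlation is modelled correctly. A simple on/off contrast shows higher power (95–100%), but only by assuming no carryover, so it is not the benchmark for this model.
3. State that the overall early-versus-late mean over months 0–12 is not a test of FMT.

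The cost is SAP wording and model code, with the same patients and samples. There are two drawbacks. The primary contrast does not use the late group's own switch to FMT. Estimates that use months 7–12 depend on how calendar month and after-course effects are modelled, because no untreated patients remain then and only the early group supplies after-course samples.

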In the event of early termination, a visit will be performed whenever possible, including a final blood sample and all end of treatment assessments that should be completed as soon as possible. All patients with at least 1 week of treatment will be

eligible for analysis.

Number of Patients:

A maximum of 40 patients will be enrolled in intervention part of this study and randomized 1:1 into one of the two groups [20 patients per group] using an internet based randomizer software [<https://www.randomizer.org/>]. We may screen up to an extra 10 patients to compensate for possible drop outs, withdraw consent or those who discontinued for any other reason.

We will also recruit up to 10 healthy volunteers to provide a blood sample [1 tube, 5 ml] to serve as a reference arm for the cytokine analysis. This reference group will be seen only once and will not participate in any other study activities.

Consequently, the total number of participants in this study will be n=50.

Inclusion criteria for patients:

1. Have a confirmed diagnosis of relapsing MS defined by the 2010 Revised McDonald Criteria for the Diagnosis of Multiple Sclerosis¹
2. Have a baseline Expanded Disability Status Scale (EDSS) ≤ 7.0
3. Age equal or older than 18 years of age
4. Be able to attend all clinic appointments without interruption
5. Be proficient in English
6. Be willing and able to give written informed consent
7. Negative blood pregnancy test at screening

Exclusion criteria for patients

1. Not meeting all of the above inclusion criteria
2. Pregnancy [current or planned for the near future] or breastfeeding
3. All qualified patients will not be currently or recently [90 days] treated with immunosuppressive therapy [i.e. chemotherapy] or high dose corticosteroids [i.e. 1g of prednisone or greater or equivalent]. Immune-Modulatory therapies are allowed as per standard of care.
4. Ongoing use of antibiotics
5. Presence of a chronic intestinal disease e.g. celiac, mal-absorption, colonic tumor
6. Concomitant inflammatory diseases
7. Standard of care exclusions for MRI scans as per LHSC standards

Healthy controls Selection:

1. Age equal or older than 18
2. Written informed consent
3. Self reportedly “healthy”, in particular not having a history of any disease or

disorder, or any treatment ever for such [ie lupus, cancer, etc], that in the opinion of the PI could be possibly related to changes in the immune system that would alter the results of a cytokine in blood analysis.

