6.2.3 Peripheral blood cytokines levels

Cytokine levels will be measured as previously described⁷². Peripheral blood will be collected into EDTA blood collection tubes ensuring complete mixing with anticoagulant to avoid clotting. Within 60 minutes of blood collection samples will be spun for 10 minutes at 4500xg. The plasma will be collected and aliquoted into cryovials. All samples will be collected and stored at -80°C before the plasma is measured for 25 immunological cytokines using a luminex-based multiplexed immunoassay. The Human Th17 Magnetic bead panel (HTH17MAG-14K, Millipore) will be used in this study to detect changes in Interleukin 1 β (IL-1 β), IL-2, IL-4, IL-5, IL-6, IL-9, IL-10, IL-12p70, IL-13, IL-15, IL-17A, IL-17E/IL-25, IL-17F, IL-21, IL-22, IL-23, IL-27, IL-28A, IL-31, IL-33, granulocyte macrophage colony stimulating factor (GM-CSF), interferon γ (IFN γ), macrophage inflammatory protein 3 α (MIP-3 α), tumour necrosis factor α (TNF α) and TNF β . Plasma samples will be run in duplicate and assays will be standardized as per product specifications. Plasma cytokine levels in healthy controls will be compared to levels in MS patients at all time points. Moreover, cytokine levels of MS patients at baseline (D0) will be compared to levels at 12 months to determine whether intervention (FMT) had an effect on pro- and anti-inflammatory cytokine levels.

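### Section 9.3 names neither the FMT contrast nor a baseline covariate; in the randomised months 1–6 comparison, baseline adjustment would give more precision from the same data.

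*Combined protocol and SAP*

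**What the plan says.** The efficacy analysis is section 9.3 (Biomarkers) alone: "We will analyze mean differences between two independent groups whilst subjecting participants to repeated measures overtime", followed by "Therefore, we will use the mixed-design ANOVA model". It names no covariate, does not list the levels of the time factor, and does not say whether group, visit or their interaction answers the FMT question, or over which months.

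Two other sections describe the cytokine outcome. Section 7.0 gives "Changes in peripheral blood cytokines within RMS patients between baseline and months 1 to 12 inclusive, for both groups". Section 6.2.3 says that "cytokine levels of MS patients at baseline (D0) will be compared to levels at 12 months". Section 6.2.1 and Tables 1 and 2 schedule a baseline cytokine sample for every patient in both groups.

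On size, the synopsis states "A maximum of 40 patients will be enrolled in intervention part of this study and randomized 1:1 into one of the two groups". Section 6.3 adds "It was assumed that the acceptable Type I error will be 0.05 and power will be 0.8", "Moderate effect size effect is expected" and "a 40% change in cytokine levels (ie TGFbeta1) analysis is expected". Section 9.1 describes the number per group as arbitrary.

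**The concern.** The outcome is defined relative to baseline, but nothing in the plan uses baseline for adjustment. If baseline is simply one level of the time factor, the group difference in change is a change-score comparison. It subtracts each patient's whole baseline deviation, however weakly baseline predicts later values. Regressing on baseline subtracts only the predictive part.

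With 20 per group and no derived sample size, there is no planned margin to absorb an avoidable loss of precision. What is at stake is power and interval width. The planned comparison is not biased by this choice.

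**Working it through.** **Inputs from the documents:** 20 per group; alpha 0.05; target power 0.80; a moderate effect with no number; monthly cytokine samples taken before that visit's FMT. The early group has FMT at months 0–5 and the late group at months 6–11. The late group's samples at months 1–6 are therefore all pre-FMT.

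**Assumptions, not in the documents:** moderate means 0.5 SD of a single-visit value, sustained over months 1–6; two-sided test; unit variance; the same correlation ρ between any two visits. ρ is unknown, so a range is shown.

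**The plan's own figure.** The 20 per group cannot be reproduced, because no SD or derivation is given.
- For d = 0.5, n per group = 2(1.96 + 0.84)²/0.5² ≈ 63.
- A 40% change gives 20 per group only if the SD is about 45% of the mean (0.40/0.45 ≈ 0.89 SD).

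**Formulas** for the mean of k post-baseline visits, per patient:
- V(post) = (1 + (k−1)ρ)/k
- V(change) = V(post) + 1 − 2ρ
- V(ANCOVA) = V(post) − ρ²
- Non-centrality = 0.5/√(2V/20); power comes from the non-central t distribution.

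Example, k = 6, ρ = 0.5:
- V(post) = 3.5/6 = 0.583
- V(change) = 0.583 + 1 − 1 = 0.583, non-centrality 2.07, power 52%
- V(ANCOVA) = 0.583 − 0.25 = 0.333, non-centrality 2.74, power 76%

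| ρ | Months 1–6 mean: V change / ANCOVA | ratio | power change / ANCOVA | Single visit: V change / ANCOVA | ratio | power change / ANCOVA |
|---|---|---|---|---|---|---|
| 0.3 | 0.817 / 0.327 | 2.50 | 40 / 77% | 1.40 / 0.91 | 1.54 | 26 / 37% |
| 0.5 | 0.583 / 0.333 | 1.75 | 52 / 76% | 1.00 / 0.75 | 1.33 | 34 / 43% |
| 0.7 | 0.350 / 0.260 | 1.35 | 74 / 86% | 0.60 / 0.51 | 1.18 | 51 / 58% |
| 0.9 | 0.117 / 0.107 | 1.09 | 99.5 / 99.7% | 0.20 / 0.19 | 1.05 | 93 / 94% |

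To match ANCOVA of the months 1–6 mean at 20 per group, the change contrast needs about 20 × 1.75 = 35 per group at ρ = 0.5, or 20 × 1.35 = 27 at ρ = 0.7.

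**Other readings of 9.3 over the same window**, power at ρ = 0.3 / 0.5 / 0.7 / 0.9:
- Group main effect over baseline and months 1–6: 55 / 42 / 34 / 28%.
- Months 1–6 only, no covariate: 67 / 52 / 43 / 36%.
- Omnibus group-by-visit F test, baseline to month 6 (4,000 simulated trials): 20 / 27 / 47 / 95%, against simulated ANCOVA at 76 / 74 / 85 / 99.6%.

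ANCOVA has the highest power in each case, so the result does not hinge on baseline being a level of the time factor.

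**All 13 visits.** With an immediate, fully reversible effect, the generalised least squares variance of an on/off FMT contrast is the same with and without baseline as a covariate (ratio 1.000 at each ρ; for example 0.00417 both ways at ρ = 0.5). On the same assumption the group main effect over all 13 visits rejects in about 5% of simulated trials, the nominal error rate, because both groups receive six FMT months. The omnibus interaction rejects in at least 99.8%. The choice of term and months therefore matters even more than the covariate.

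**The case against.** Several objections stand and limit the point.

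- A reader might infer that section 9.3 itself makes baseline an outcome level. It does not list the levels; this is an inference from 9.3 and 7.0 together.
- Keeping baseline among the outcomes is not in itself a fault. A repeated-measures model with a common baseline mean across groups is about as efficient as ANCOVA in large samples. The loss comes from the unconstrained contrast.
- The mean of months 1–6 is not an endpoint that the documents define, and it shows a larger gain than a single visit at each ρ in the table.
- It is tempting to say that ANCOVA is never less precise. That holds when the slope is known. Estimating it in 40 patients inflates the variance by about 1/36, roughly one point of power here, and can erase the single-visit gain at very high ρ.
- A reader might also expect unusually large chance imbalance for cytokines. Nothing in the documents supports that. Under 20 v 20 randomisation the standard error of any baseline difference is √(2/20) = 0.32 SD.
- This is an exploratory proof-of-concept study, and the planned analysis would be inefficient rather than biased.

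The objection that adjustment gains nothing over all 13 visits is correct only without carry-over. Section 4.2 provides no washout, and section 6.2.5 treats the time for recipients to return to their original microbiota as a question to be studied. Absence of carry-over therefore cannot be assumed.

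**Conclusion.** The point holds for the randomised months 1–6 comparison. Section 9.3 leaves the FMT contrast undefined and plans no baseline adjustment.

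Under the stated assumptions, adjustment raises power over the change contrast by 37, 24 and 12 points for the months 1–6 mean at ρ = 0.3, 0.5 and 0.7. For a single visit the gain is 11, 9 and 7 points. At ρ = 0.9 it is about 0.2 and 1 point.

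The direction is secure across this range. The size rests on ρ, d = 0.5 and compound symmetry, none of which the documents supply. The documents do not support a claim of bias, or of a gain under every possible contrast.

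**What to change.** In section 9.3:

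1. Name early v late over months 1–6 as the FMT comparison for each analyte.
2. Adjust for that analyte's baseline. Use ANCOVA of the months 1–6 mean, or a repeated-measures model with baseline as covariate or with a common baseline mean across groups.
3. Report the adjusted group difference with its 95% CI.
4. Analyse months 7–12 separately, as supportive.
5. For gut permeability, use ANCOVA of the month-6 value on baseline. Only the smaller single-visit gain applies there.

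The cost is wording in the plan and one slope per analyte for ANCOVA, or up to six baseline coefficients if baseline-by-visit terms are fitted over months 1–6. No extra patients, visits or samples are needed.
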